11. STUDY TERMINATION

The occurrence of one or more Unanticipated Serious Adverse Device Effect (USADE), or any SAE where the relationship to study agent cannot be ruled out, may result in stopping further dispensing of test article. In the event of a USADE or SAE, the Sponsor may unmask the treatment regimen for the subject(s) and will discuss this with the Investigator before any further subjects are enrolled.

The Sponsor will determine when a study will be stopped. The Principal Investigator always has the discretion to initiate stopping the study based on patient safety or if information indicates the study's results are compromised.

JJVC reserves the right to terminate the study at any time for any reason. Additionally, the IEC/IRB reserves the right to terminate the study if an unreasonable risk is determined. The study can be terminated by the Principal Investigator at the individual clinical site due to specific clinical observations, if in their opinion, after a discussion with JJVC, it is determined that it would be unwise to continue at the clinical site.

JJVC (and the IEC/IRB and DMC, if applicable) will evaluate all adverse events. If it is determined that an adverse event presents an unreasonable risk, the investigation, or that part of the investigation presenting the risk, will be terminated, as soon as possible.

Should the study be terminated (either prematurely or as scheduled), the Investigator will notify the IEC/IRB and Regulatory Authority as required by local regulatory requirements.

12. PROCEDURE FOR HANDLING PRODUCT QUALITY COMPLAINTS

A Product Quality Complaint (PQC) refers to any written, electronic, or oral communication that alleges deficiencies related to the identity, quality, durability, reliability, safety, effectiveness or performance of test articles after they have been released for clinical trial use.

Potential complaints may come from a variety of sources including but not limited to subjects, clinical research associates (CRA), clinical operations managers (COM), medical monitors, and site personnel, etc. The following are not considered product quality complaints:

- Subject satisfaction inquiries reported via “Subjective Questionnaires” and “Patient Reported Outcomes (PRO)”.
 - Clinical test articles that are stored improperly or damaged after receipt at the investigational site.
 - Lens replacements that occur due to drops/fall-outs.
 - Damage deemed by clinicians or clinical staff to be caused by handling by the user, and not indicative of a quality deficiency (i.e. tears, rips, etc.), only in situations where there is no deficiency alleged by the subject.

Within 24 hours of site personnel becoming aware that a PQC has occurred, the PQC must be recorded in the EDC system, which will trigger an automatic email notification to the appropriate COM/CRA and Clinical QA representative. In cases where the EDC system in use is not configured to send automatic notifications or when an EDC system is not used, the COM/CRA is responsible for notifying Clinical QA upon discovery that a PQC has occurred.

Upon receipt of the EDC notification, the COM/CRA will contact the study site to collect additional information which will include:

- Date the complaint was received/recorded in the EDC System (Date of Sponsor Awareness)
- Who received the complaint
- Study number
- Clinical site information (contact name, site ID, telephone number)
- Lot number(s)
- Unique Subject Identifier(s)
- Indication of who first observed complaint (site personnel or subject)
- OD/OS indication, along with whether or not the lens was inserted
- Any related AE number if applicable
- Detailed complaint description (scheduled/unscheduled visit, wear time, symptoms, resolution of symptoms, etc.)
- Eye Care Provider objective (slit lamp) findings if applicable
- Confirmation of product availability for return (and tracking information, if available), or rationale if product is not available for return

Once a complaint is received, it will be assessed by the COM, CRA, or trained site personnel to determine if it is an Adverse Event/Serious Adverse Event (AE/SAE). If the complaint results in an AE/SAE, the COM/CRA, or trained site personnel will follow Section 13 of this protocol. If the AE/SAE was potentially the result of a product quality related deficiency, these procedures also applies and will be executed in parallel.

In some cases, a PQC form may be generated in EDC by the site in error. In this event, the PQC forms will be marked “Intentionally Left Blank” or “ILB”. Justification for ILB must be documented.

13. ADVERSE EVENTS

13.1. Definitions and Classifications

Adverse Event (AE) – An AE is any untoward (unwanted) medical occurrence in a patient or clinical investigation subject administered a test article, study treatment or study procedure whether or not caused by the test article, study treatment or procedure. An AE can therefore be any unfavorable or unintended sign (including an abnormal finding), symptom, or disease temporally associated with the use of the test article, study treatment, or study procedure whether or not related to the test article, study treatment, or study procedure.

An AE includes any condition (including a pre-existing condition) that:

1. Was not present prior to the study, but appeared or reappeared following initiation of the study
2. Was present prior to the study, but worsened during the study. This would include any condition resulting from concomitant illnesses, reactions to concomitant medications, or progression of disease states
3. Pregnancy must be documented as an adverse event and must be reported to the clinical monitor and to the Sponsor immediately upon learning of the event

Serious Adverse Event (SAE) – An SAE is any untoward medical occurrence that:

- Results in death
- Is life threatening
- Requires in-patient hospitalization or prolongation of existing hospitalization
- Results in persistent or significant disability/incapacity (e.g., a sight threatening event, a significant persistent or permanent change, impairment, damage, or disruption to the subject’s body)
- Is a congenital anomaly/birth defect, or
- Requires intervention to prevent permanent damage (the use of the test article resulting in a condition which requires medical or surgical intervention to preclude permanent impairment of the body structure or a body function). Important medical events that may not result in death, be life-threatening, or require hospitalization may be considered an SAE when, based upon appropriate medical judgment, they may jeopardize the patient or subject and may require medical or surgical intervention to prevent one of the outcomes listed in the above definition.

Diagnoses and conditions that are considered Ocular Serious Adverse Events include, but not limited to:

- Microbial Keratitis (MK)
- Iritis (including cells in the anterior chamber)
- Permanent decrease in best spectacle corrected visual acuity equivalent to 2 acuity lines or greater

- Central Corneal Opacity
- Central Corneal Neovascularization
- Uveitis
- Endophthalmitis
- Hypopyon
- Hyphemia
- Penetration of Bowman's Membrane
- Persistent Epithelial Defect
- Limbal cell Damage leading to Conjunctivalization

Significant Adverse Events – Those events that are usually symptomatic and warrant discontinuation (temporary or permanent) of the test article (excluding Serious Adverse Events).

Diagnoses and conditions that are considered Ocular Significant Adverse Events include, but not limited to the following:

- Contact Lens Induced Peripheral Ulcer (CLPU)
- Significant Infiltrative Events (SIE)
- Superior Epithelial Arcuate Lesions (SEALS)
- Any Temporary Loss of >2 Lines of BSCVA
- Other Grade 3 or higher corneal findings, such as abrasions or edema
- Non-contact lens related corneal events - e.g. Epidemic Keratoconjunctivitis (EKC)
- Asymptomatic Corneal Scar
- Any corneal event which necessitates temporary lens discontinuation >2 weeks

Non-Significant Adverse Events – Those conditions that are usually asymptomatic and usually do not warrant discontinuation (temporary or permanent) of the test article. However, the Investigator may choose to treat as a precautionary measure.

Diagnoses and conditions that are considered Ocular Non-Significant Adverse Events include, but not limited to the following:

- Non-significant Infiltrative Event (NSIE)
- Contact Lens Papillary Conjunctivitis (CLPC)
- Superficial Punctate Keratitis (SPK)
- Conjunctivitis: Bacterial, Viral, Allergic
- Blepharitis
- Meibomianitis
- Contact Dermatitis
- Localized Allergic Reactions
- Any corneal event not explicitly defined as serious or significant adverse event, which necessitates temporary lens discontinuation <2 weeks

Adverse Device Effect (ADE) – A sub-set of AEs, and include only those adverse events that are cause by or related to the investigational device.

Unanticipated Adverse Device Effect (UADE) – Any serious adverse effect on health or safety or any life-threatening problem or death caused by, or associated with, the test article, if that effect, problem, or death was not previously identified in nature, severity, or degree of incidence in the investigational plan, Investigator's Brochure or protocol, or any other unanticipated serious problem associated with the test article that relates to the rights, safety and welfare of subjects.

13.2. Assessing Adverse Events

In conjunction with the medical monitor, the Investigator will evaluate adverse events to ensure the events are categorized correctly. Elements of categorization will include:

- Seriousness/Classifications (see definition in Section 13.1)
- Causality or Relatedness – i.e. the relationship between the test article, study treatment or study procedures and the adverse event (not related; doubtful; possible; probable; very likely - see definition in Section 13.2.1)
- Adverse Event Severity – Adverse event severity is used to assess the degree of intensity of the adverse event (mild; moderate; severe for all events - see definition in Section 13.2.2).
- Outcome – Not Recovered or Not Resolved; Recovering or Resolving; Recovered or Resolved with Sequelae; Recovered or Resolved; Death Related to Adverse Event; Unknown
- Actions Taken – None; temporarily discontinued; permanently discontinued; other action taken

13.2.1 Causality Assessment

Causality Assessment – A determination of the relationship between an adverse event and the test article, study treatment, or study procedure. The test article, study treatment or study procedure relationship for each adverse event shall be determined by the Investigator using these explanations:

- Not Related- An adverse event that is not related to the use of the test article, study treatment or study procedures.
- Unlikely Related – An adverse event for which an alternative explanation is more likely, e.g. concomitant treatment, concomitant disease(s), or the relationship of time suggests that a causal relationship is not likely.
- Possibly Related – An adverse event that might be due to the use of the test article, or to the study treatment or study procedures. An alternative explanation, e.g. concomitant treatment, concomitant disease(s), is inconclusive. The relationship in time is reasonable. Therefore, the causal relationship cannot be excluded.
- Related – An adverse event that is listed as a possible adverse effect (device) or adverse reaction (drug) and cannot be reasonably explained by an alternative explanation, e.g. concomitant treatment of concomitant disease(s). The relationship in time is very suggestive, e.g. it is confirmed by de-challenge and re-challenge.

13.2.2 Severity Assessment

Severity Assessment – A qualitative assessment of the degree of intensity of an adverse event as determined by the Investigator or reported to him/her by the subject. The assessment of severity is made irrespective of test article, study treatment or study procedure relationship or seriousness of the event and should be evaluated according to the following scale:

- Mild – Event is noticeable to the subject, but is easily tolerated and does not interfere with the subject's daily activities
- Moderate – Event is bothersome, possible requiring additional therapy, and may interfere with the subject's daily activities
- Severe – Event is intolerable, necessitates additional therapy or alteration of therapy and interferes with the subject's daily activities

13.3. Documentation and Follow-Up of Adverse Events

The recording and documenting of adverse events (ocular and non-ocular) begins when the subjects are exposed to the test article, study treatment or study procedure. Adverse events reported before the use of test article, start of study treatment, or study procedures will be recorded as medical history. However, if the condition deteriorates at any time during the study it will be recorded and reported as an AE. Untoward medical events reported after the subject's exit from the study will be recorded as adverse events at the discretion of the Investigator.

Upon finding an adverse event, the Principal Investigator will document the condition in the subject record and in the eCRFs. He/she will complete the Adverse Event /eCRF.

Complete descriptions of all adverse events must be available in the subject record. All Adverse Events including local and systemic reactions not meeting the criteria for "serious adverse events" shall be captured on the appropriate case report form or electronic data system. All adverse events occurring while the subject is enrolled in the study must be documented appropriately regardless of relationship.

It is the Investigator's responsibility to maintain documentation of each reported adverse event. All adverse events will be followed in accordance with applicable licensing requirements. Such documentation will include the following:

- Adverse event (diagnosis not symptom)
- Drawings or photographs (where appropriate) that detail the finding (e.g., size, location, and depth, etc.)
- Date the clinical site was notified
- Date and time of onset
- Date and time of resolution
- Adverse event classification, severity, and relationship to test articles, as applicable
- Treatment regimen instituted, including concomitant medications prescribed, in accordance with applicable licensing requirements
- Any referral to another health care provider if needed
- Outcome, ocular damage (if any)
- Likely etiology

- Best corrected visual acuity at the discovery of the event and upon conclusion of the event

In addition, if an infiltrate(s) is present, he/she will complete the Corneal Infiltrate Assessment /eCRF. Where necessary, a culture of the corneal lesion will be collected to determine if the infection is microbial in nature. If cultures are collected, the date of culture collection and laboratory utilized will be recorded.

Changes in the severity of an AE shall be documented to allow an assessment of the duration of the event at each level of intensity to be performed. Adverse events characterized as intermittent require documentation of the onset and duration of each episode. Changes in the assessment of relationship to the Test Article shall also be clearly documented.

Subjects who present with an adverse event shall be followed by the Investigator, within licensure, until all signs and symptoms have returned to pre-treatment status, stabilized, or been satisfactorily resolved. If further treatment beyond licensure is required, the patient will be referred to the appropriate health care provider. The Investigator will use his/her clinical judgment as to whether or not a subject reporting with an adverse event will continue in the study. If a subject is discontinued from the study, it will be the responsibility of the Investigator to record the reason for discontinuation. The Investigator will also document the adverse event appropriately and complete the Adverse Event /eCRF. Any subjects with ongoing adverse events related to the test article, study treatment or study procedures, as of the final study visit date should be followed to resolution of the adverse event or until referral to an appropriate health care provider, as recommended by the Investigator.

13.4. Reporting Adverse Events

The Investigator will notify the Sponsor of an adverse event by e-mail, facsimile, or telephone as soon as possible and no later than 24 hours from discovery for any serious /significant adverse events, and 2 days from discovery for any non-significant adverse event. In addition, a written report will be submitted by the Principal Investigator to the IEC/IRB according to their requirements (Section 13.4.2). The report will comment whether or not the adverse event was considered to be related to the test article, study treatment or study procedures.

13.4.1 Reporting Adverse Events to Sponsor

Serious/Significant Adverse Events

The Investigator will inform the sponsor of all serious/significant adverse events occurring during the study period as soon as possible by e-mail, fax, or telephone, but no later than 24 hours following discovery of the event. The Investigator is obligated to pursue and obtain information requested by the Sponsor in addition to that information reported on the eCRF. All subjects experiencing a serious/significant adverse event must be followed up and all outcomes must be reported.

When medically necessary, the Investigator may break the randomization code to determine the identity of the treatment that the subject received. The Sponsor and study monitor should be notified prior to unmasking the test articles.

In the event of a serious/significant adverse event, the Investigator must:

- Notify the Sponsor immediately
- Obtain and maintain in the subject's records all pertinent medical information and medical judgment for colleagues who assisted in the treatment and follow-up of the subject
- Provide the Sponsor with a complete case history which includes a statement as to whether the event was or was not related to the use of the test article
- Notify the IEC/IRB as required by the IEC/IRB reporting procedure according to national regulations

Unanticipated (Serious) Adverse Device Effect (UADE)

In the event of an Unanticipated (Serious) Adverse Device Effect (UADE), the Investigator will submit a report of the UADE to the Sponsor and IEC/IRB as soon as possible, but no later than 24 hours after the Investigator first learns of the effect. This report is in addition to the immediate notification mentioned above.

The Sponsor must conduct an evaluation of the UADE and must report the results of the evaluation to FDA, the IEC/IRB and participating Investigators within 10 working days after the Sponsor first receives notification of the effect.

Non-Serious Adverse Events

All non-serious adverse events, including non-serious adverse device effects, will be reported to the sponsor by the Investigator no later than 2 days from discovery.

13.4.2 Reporting Adverse Events to the Responsible IEC/IRB and Health Authorities

Adverse events that meet the IEC/IRB requirements for reporting must be reported within the IEC/IRB's written guidelines. Each clinical site will refer to and follow any guidelines set forth by their Approving IEC/IRB. Each clinical site will refer to and follow any guidelines set forth by their local governing Health Authorities.

The Sponsor will report applicable Adverse Events to the local health authorities according the written guidelines, including reporting timelines.

13.5. Event of Special Interest

Not applicable.

13.6. Reporting of Pregnancy

Subjects reporting pregnancy (by self-report) during the course of the study will be discontinued after the event is recorded as an Adverse Event. Once discontinued, pregnant participants and their fetuses will not be monitored for study related purposes. At the Investigator's discretion, the study participant may be followed by the Investigator through delivery. However, this data will not be collected as part of the clinical study database. Pregnant participants are not discontinued from contact lens or solution related studies for safety concerns, but due to general concerns relating to pregnancy and contact lens use. Specifically, pregnant women are discontinued due to fluctuations in refractive error and/or

visual acuity that occur secondary to systemic hormonal changes, and not due to unforeseen health risks to the mother or fetus.

14. STATISTICAL METHODS

14.1. General Considerations

Statistical Analysis will be undertaken by the sponsor. A general description of the statistical methods to be implemented in this clinical trial is outlined below.

All data summaries and statistical analyses will be performed using the SAS software Version 9.4 (*SAS Institute, Cary, NC*). Throughout the analysis of data, the results for each subject/eye will be used when available for summarization and statistical analysis. Unscheduled visits will be summarized separately and will be excluded from the statistical analysis.

Summary tables (descriptive statistics and/or frequency tables) will be provided for all baseline variables, efficacy variables and safety variables as appropriate. Continuous variables will be summarized with descriptive statistics (n, mean, standard deviation (SD), median, minimum and maximum). Frequency count and percentage of subjects or eyes within each category will be provided for categorical data.

14.2. Sample Size Justification

There will be one testing site: VRC [REDACTED] A total of approximately 45 eligible subjects will be enrolled into the study at this site. At least 42 subjects will complete this study. The sample size to complete the study is based on the primary hypothesis selected based on the results of a prior Repeatability & Reproducibility (R&R) study regarding ETDRS visual acuity test. The R & R study is a post-hoc analysis of two studies CR-1619 and CR-1622.

Using the POWER procedure in SAS 9.4, below is the summary of sample size required based on the different assumptions of the true difference in electronic LogMAR visual acuity. The sample size was calculated for the non-inferiority tests with at least 90% of statistical power and 2-sided type I error of 0.05. The intraclass correlation was assumed to be 0.5.

Assuming the true difference in electronic LogMAR visual acuity is between 0 (no difference) to 0.02 (one letter), it requires 24 to 63 independent eyes to demonstrate non-inferiority.

- Electronic LogMAR visual acuity

Difference (Test-Control)	Estimated Standard Deviation	# of eyes needed	Power
0.00	0.08	24	0.9
0.02	0.08	63	0.9

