2.3. Hypotheses

Primary Hypotheses

HLLC and LLHC electronic logMAR Visual Acuity of ACUVUE OASYS® Brand Contact Lenses 1-Day with HydraLuxe™ Technology (AO1D) will be non-inferior to that of best corrected spherocylindrical refraction with trial frame (SCR). A non-inferiority margin of 0.05 (2 and half letters) is assumed.

Secondary Hypotheses

The area under log of the contrast sensitivity function will not be statistically different for ACUVUE OASYS® Brand Contact Lenses 1-Day with HydraLuxe™ Technology compared to best corrected spherocylindrical refraction.

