14.5. Primary Analysis

Electronic LogMAR Visual Acuity will be analyzed on the analysis population using a linear mixed model. The model will include the experimental design factors: visit, test condition (AO1D/SCR), sequence of the test conditions as fixed effects. Subject will be included as a random effect. Age and gender will be included as fixed covariates when appropriate. The covariance between residual errors from the same subject across test conditions for the same test method will be selected based on the finite-sample corrected Akaike's Information Criterion³. Covariance structures considered may include: Homogenous compound symmetry (CS) and Unstructured covariance structure (UN). The structure that returns the lowest Akaike Information Criteria Corrected (AICC) will be selected as the structure that best fit the data.

Comparisons among the test conditions will be carried out using 95% confidence intervals constructed of pairwise least-square means (LSM) differences from the linear mixed model. Non-inferiority will be established if the upper confidence limit is less than 0.05. If non-inferiority is attained, superiority will be tested. Superiority will be concluded if upper confidence limit is less than 0.

In all models, the Kenward and Roger method (Kenward and Roger, 1997)⁴ will be used for the calculation of the denominator of degrees of freedom.

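### Section 14.2's 24 and 63 independent eyes belong to a one-sided 0.05 test; at the stated 2-sided 0.05 and the 95% CI rule, 29 and 77 are needed

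*Combined protocol and SAP*

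**What the plan says.** Section 2.3 sets the margin: "A non-inferiority margin of 0.05 (2 and half letters) is assumed". Section 14.2 gives the error rate and power: "The sample size was calculated for the non-inferiority tests with at least 90% of statistical power and 2-sided type I error of 0.05". With an estimated standard deviation of 0.08 in both rows of its table, it concludes that "it requires 24 to 63 independent eyes to demonstrate non-inferiority", the lower figure for a true difference of 0 and the upper for 0.02. It adds: "The intraclass correlation was assumed to be 0.5". The planned size is 45 subjects enrolled and at least 42 completing.

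Section 14.5 sets the decision rule. "Comparisons among the test conditions will be carried out using 95% confidence intervals" of least-squares mean differences from a mixed model, and "Non-inferiority will be established if the upper confidence limit is less than 0.05". On the unit of analysis, Section 14.1 says that "the results for each subject/eye will be used when available for summarization and statistical analysis", and Section 14.5 says "Subject will be included as a random effect". Section 7.2 (steps 2.11 and 3.11) has right and left eyes tested separately under each condition.

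**The concern.** The upper limit of a two-sided 95% confidence interval falls below the margin by chance with probability 0.025 at the margin, not 0.05. The 2-sided 0.05 of Section 14.2 means the same thing, so the stated level and the decision rule agree. The tabulated eye counts looked too small for that level.

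If they are, the 90% power in the table was calculated for a more lenient test than the one the trial will run. The table also counts independent eyes, while the trial contributes two eyes per subject. The margin of safety between 84 tested eyes and the required number therefore depends on which required number is correct. A result near a true difference of 0.02 that just missed non-inferiority would be read against a 90% figure that does not belong to the rule used.

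**Working it through.** **Inputs.** Margin 0.05 (Section 2.3); true difference d = 0 or 0.02, SD 0.08, ICC 0.5 and power 0.90 (Section 14.2); 2x2 crossover, so one paired difference per eye (Section 4.2); upper limit of a 95% CI (Section 14.5).

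**SD of the paired difference.** If the ICC of 0.5 is the correlation between the two conditions, SD = 0.08 × √(2 × (1 − 0.5)) = 0.08. If it is the correlation between fellow eyes, 0.08 is taken directly as the SD of the difference. Both readings give 0.08.

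**Formula.** Paired non-inferiority t-test on n independent eyes: df = n − 1, noncentrality = (0.05 − d)/0.08 × √n, power = P(noncentral t > t critical at one-sided α). The required n is the smallest with power of at least 0.90.

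**Step 1: reproduce the table.** At one-sided α = 0.05:

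| d | n | Power at n | Power at n − 1 |
|---|---|---|---|
| 0 | 24 | 0.907 | 0.896 |
| 0.02 | 63 | 0.903 | 0.899 |

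Both rows match the plan exactly.

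**Step 2: the stated level.** At one-sided α = 0.025:

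| d | n | Power at n | Power at n − 1 |
|---|---|---|---|
| 0 | 29 | 0.901 | 0.890 |
| 0.02 | 77 | 0.901 | 0.897 |

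**Step 3: power of the tabulated counts under the 95% CI rule.**

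- 24 eyes, d = 0: noncentrality 0.05/0.08 × √24 = 3.06, critical value 2.069, power 0.834.
- 63 eyes, d = 0.02: noncentrality 0.03/0.08 × √63 = 2.98, critical value 1.999, power 0.834.

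With 63 eyes, 90% power is kept only up to a true difference of 0.0168.

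**Step 4: can another reading of the SD rescue 24 and 63 at one-sided 0.025?**

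| SD of difference | n at d = 0 | n at d = 0.02 |
|---|---|---|
| 0.08 × √2 = 0.113 | 56 | 152 |
| 0.08 | 29 | 77 |
| 0.08 × √0.5 = 0.057 | 16 | 40 |

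None does. It would take an SD of about 0.072, which Section 14.2 does not give.

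**Step 5: what 42 completers provide.** Let r be the between-eye correlation of the treatment differences. The plan does not state r, so the range 0 to 1 is an assumption. The SD of a subject's mean difference over two eyes is 0.08 × √((1 + r)/2), so 42 subjects are worth 84/(1 + r) independent eyes. With df = 40 for the two-sequence crossover and one-sided 0.025, per-endpoint power at d = 0.02 is:

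| r | Power |
|---|---|
| 0 | 0.918 |
| 0.07 | 0.900 |
| 0.1 | 0.892 |
| 0.2 | 0.865 |
| 0.5 | 0.782 |
| 1 | 0.660 |

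Simulation of the crossover (40,000 trials per value of r) agrees: 0.919, 0.901, 0.894, 0.865, 0.785 and 0.660. At d = 0, power runs from 0.9999 (r = 0) to 0.977 (r = 1).

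**Step 6: what the error does to the safety margin.** Setting 84/(1 + r) equal to the required count gives 84/63 − 1 = 0.33 for the plan's figure and 84/77 − 1 = 0.09 for the corrected one. The exact break-even with df = 40 is 0.07.

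**The case against.** The best defence is that the trial is not sized at 24 or 63 eyes. It plans 84 eyes from 42 completers, more than the corrected 77, and the 83.4% is the power of the tabulated counts, not of the trial. At a true difference of 0, power is at least 0.977 whatever r is. At 0.01 it is 0.994 for r = 0, 0.955 for r = 0.5 and 0.885 for r = 1. Type I error, margin, decision rule and conduct are untouched. All of this is true, and it confines the practical exposure to the 0.02 end of the assumed range. It does not make the table right, and 84 correlated eyes cannot be set against a count of independent eyes without a value for r.

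A second point is that 29 and 77 may themselves be incomplete. Section 14.4 announces a simulation-based multiplicity adjustment, and the primary endpoint is tested under two conditions, HLLC and LLHC. If the intervals were widened for that, more eyes would be needed; a Bonferroni level of 0.0125 would give 35 and 91. If both conditions must succeed, per-endpoint power overstates joint power: under independence at r = 0 it is about 0.918² = 0.84. Section 14.4 does not say that its adjustment changes the Section 14.5 interval, so 29 and 77 are the answers at the level Section 14.2 states. The power figures above are per endpoint and should be read that way.

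Third, the contradiction could instead be removed by relabelling the level as one-sided 0.05. That would also require changing the 95% interval in Section 14.5. Since the text of Section 14.2 and the rule in Section 14.5 already agree, the table is the part to correct.

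Finally, reading 0.08 as the SD of the paired difference is an inference, but it is the only reading tried that reproduces both rows exactly.

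**Conclusion.** The concern holds. The two eye counts in Section 14.2 are wrong for the level stated beside them and for the decision rule in Section 14.5. They are short by 5 eyes (24 against 29) and 14 eyes (63 against 77), or 21% and 22%, and power is 83.4% where 90% is claimed. This rests on the paired t-test with an SD of the difference of 0.08 and no multiplicity adjustment.

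It does not follow that the trial is underpowered. With 42 completers, 90% power at a true difference of 0.02 is reached if r is about 0.07 or less and missed if r is larger. The document does not let a reader tell which. The single ICC of 0.5 is not tied to conditions or to fellow eyes, and no conversion from eyes to subjects is shown. If 0.5 were the between-eye correlation of the differences (an assumption), 42 subjects would equal 84/1.5 = 56 independent eyes, with power of about 0.78.

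**What to change.** In Section 14.2:

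- Replace 24 and 63 with 29 and 77 independent eyes, and state the level as one-sided 0.025, the equivalent of the 95% upper limit in Section 14.5.
- State what the intraclass correlation of 0.5 correlates.
- Show the conversion from eyes to subjects, for example 42 subjects = 84/(1 + r) independent eyes, and give r or a range for it from the repeatability and reproducibility data.
- Restate the per-endpoint power of 42 completers at a true difference of 0.02 over that range (0.92 at r = 0, 0.90 at 0.07, 0.78 at 0.5, 0.66 at 1).
- Say whether the Section 14.4 adjustment applies to HLLC and LLHC. If it does, recalculate at the adjusted level.

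Enrolment, the margin and the decision rule stay as they are. The change is to text only; its cost is a less favourable stated power at the 0.02 end.
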